### 7.10 End of Treatment (EOT) and Follow Up

The end of treatment/follow up column will be utilized for subjects that come off protocol therapy (radium-223 dichloride if randomized to that Arm and ADT) for toxicity or progression. If this occurs, subjects should have an end of treatment visit 30 days ( $\pm$  7 days) after discontinuation of protocol therapy. Subjects will then continue to be followed every 3 months for a total of 2 years from the date of randomization. Follow up may occur via phone call, email or other communication. If available by medical record review, alk phos, PSA, AE/concomitant medication should be obtained. Testing to be done at the EOT visit:

- Circulating tumor cell's (CTCs)
- Serum bone turnover markers
- Banking Samples: serum, plasma
- Alkaline phosphatase
- PSA

If a subject withdraws consent, he is deemed **“off study”**. “Off study” subjects will not be followed further.

A subject will be discontinued from the protocol specified therapy under the following circumstances:

- If there is evidence of radiologic disease progression or symptomatic deterioration despite castration range serum testosterone level ( $< 50$  ng/dL). Such subjects can go on to other treatment outside the study as clinically indicated including continuation or initiation of radium-223 dichloride therapy. They will remain on follow-up portion of the study for a total of 2 years from the date of randomization.
- If there is development of castration-resistant prostate cancer by PSA criteria in conjunction with castration range serum testosterone level ( $< 50$  ng/dL). Castration resistant prostate cancer is defined as two consecutive increases in PSA over the nadir PSA, at least two weeks apart **AND** an absolute increase of at least 2 ng/mL from the nadir PSA (or from baseline PSA if there was no drop in PSA after starting treatment). Discontinuation of bicalutamide may be attempted at the investigator's discretion in such cases and would NOT constitute going “off treatment”. If no response to bicalutamide discontinuation, such subjects may receive other treatment outside the study as clinically indicated including continuation or initiation of radium-223 dichloride therapy. They will remain on follow-up portion of the study for a total of 2 years from the date of randomization.
- If a subject requests to discontinue protocol specified therapy for any reason at any time. Subjects can stop protocol therapy at any time (off treatment). Such subjects may receive other treatment outside the study as clinically indicated including continuation or initiation of radium-223 dichloride therapy. However, subjects will continue to be followed for survival status and for secondary malignancies as reported by subjects every 3 months for a total of 2 years from the date of randomization unless they withdraw consent (if consent withdrawn, they will be deemed to be off study).

- If androgen deprivation therapy exhibits unacceptable toxicity. Such subjects may receive other treatment outside the study as clinically indicated including continuation or initiation of radium-223 dichloride therapy. **NOTE:** Subjects off bicalutamide or radium-223 dichloride for toxicity but continuing on LHRH agonist/antagonist or have had surgical castration remain on protocol specified therapy.
- If **ALL** protocol specified therapy is interrupted for > 28 days due to a treatment related adverse event. **NOTE:** A delay of up to 7 days in administering the scheduled dose of LHRH agonist or LHRH antagonist is allowed. A delay of up to 56 days in administering the scheduled dose of radium-223 dichloride is allowed if it is due to inadequate hematologic parameters or drug supply issues.

All reasons for protocol therapy discontinuation must be clearly documented.

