### 5.8 Concomitant Medications

The use of supportive care medications is allowed according to institutional standards. We strongly recommend supplemental calcium 1200 mg daily and Vitamin D3 1000 IU daily.

However, certain medications are specifically disallowed.

- Five-alpha reductase inhibitors (e.g. finasteride and dutasteride) are not permitted.
- Other excluded therapies include ketoconazole, aminoglutethimide, abiraterone acetate, enzalutamide (MDV3100), diethylstilbestrol (DES), and other estrogen preparations.
- Cytotoxic chemotherapy is not allowed during protocol specified therapy.

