adjusted for potentially confounding clinical variables (including PSA, bisphosphonate use, age, race, performance status, Gleason score, and pain score, among others). The study also explored the effect of treatment on bone marker levels in week 9 (as compared to baseline) and sought to find an association between a change in marker levels and overall survival outcomes. A Cox model was fit with main effects and Bone Marker x Treatment interaction; adjusted for clinical variables, to assess the predictive value of atrasentan on overall survival. Of 1,038 subjects enrolled in SWOG S0421, 855 (91%) had baseline serum submitted, of which 778 samples (75%) were usable and subsequently analyzed. The bone turnover values (median; range) were as follows: NTX (14 nM; 9.3-23.9), BAP (64.7 u/L; 35-164), CICP (9.5 ng/mL; 6.5-17.4), & PYD (2.8 nmol/L; 2.2-3.9).

Elevated markers of bone turnover (> median value) were prognostic for overall survival in SWOG 0421. Hazard ratios are reported for a 2-fold increase in markers. Follow-up analysis revealed that subjects with high marker levels (i.e., upper 25%-ile across all markers) not only have a very poor prognosis (HR = 4.3,  $p < 0.001$ ) but also appear to have a significant survival benefit from atrasentan (interaction-HR=0.33;  $p=0.002$ ), even with highly conservative statistical analysis including Bonferroni adjustment. There were 6% (47) of the 778 subjects with a complete set of measurements on baseline markers. The HR in the high marker group was estimated at 0.34 (95% CI: 0.13, 0.89); this compares with a HR of 1.04 (95% CI: 0.86, 1.25) in the low marker group.

There was also strong evidence for a significant association between the change in bone marker concentrations from baseline to Week 9 and overall survival for all bone markers. Presently, it is unclear whether these same observations will be observed in a somewhat different subject context: i.e., in the newly diagnosed, metastatic prostate cancer setting (non-castrate resistant).

Radium-223 dichloride demonstrated similar declines in bone turnover markers in CRPC including BAP in a phase 2 clinical trial in prostate cancer and in the randomized phase 3 trial. The encouraging results from SWOG S0421 bone marker studies in CRPC and the proven effects of radium-223 dichloride on bone turnover lead us to pose several clinically relevant questions that can be prospectively explored in this study:

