- Are markers of bone metabolism of prognostic and predictive value only in the CRPC setting, or do they have value in newly diagnosed metastatic prostate cancer?
- How will this radium-223 dichloride-induced bone phenotype behave in terms of response and survival when compared to a control group that is not receiving radium-223 dichloride?
- Can we use bone turnover biomarkers to explore who will benefit from radium-223 dichloride inhibitor therapy?

**We therefore hypothesize** that baseline levels of bone metabolism markers in sera collected from subjects with newly diagnosed metastatic prostate cancer will be of strong prognostic value and will also be predictive of benefit from radium-223 dichloride in combination with androgen deprivation therapy. A secondary hypothesis is that serial assessment of these same markers will demonstrate that lower marker levels at end of treatment visit will be associated with improved survival. To explore the effects of radium-223 dichloride on bone turnover in hormone naïve prostate cancer, serum markers of bone formation and bone resorption will be analyzed before,

during and after radium-223 dichloride treatment. Exploratory analyses will be performed to correlate the changes in bone turnover markers with clinical outcomes of interest.

These will be tested through the following **Specific Aims**:

- To measure levels of selected markers of bone formation and resorption in sera in subjects enrolled in this proposed randomized Phase II trial of ADT + radium-223 dichloride versus ADT alone in subjects with newly diagnosed subjects with metastatic prostate cancer.
- To correlate the results of these marker studies with PSA response, tumor response, progression-free survival (radiographic and PSA progression free survival), and overall survival to detect prognostic (baseline or pre-treatment sera) and/or predictive value (baseline biomarker x treatment interaction; serial sera).
- To identify prognostic groups based on baseline bone markers and other clinical and disease-related factors.

**Serum biomarkers of bone turnover** for bone resorption [N-telopeptide (NTX) expressed in nM Bone Collagen Equivalents, C-collagen fragments (CTX-I EIA) expressed in ng/mL] & formation [osteocalcin (OC) expressed in ng/mL & bone alkaline phosphatase (BAP) expressed in U/L] will be measured using commercially available assays from Quidel (OC, BAP), Immunodiagnostic Systems (IDS) (CTX-I) & Osteomark (NTX).

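### End-of-treatment research bloods are drawn about 30 days after protocol therapy stops, with no rule that they precede the next treatment, so some can reflect that treatment

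*Combined protocol and SAP*

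**What the plan says.** **Timing of the draw.** Section 7.10 states: "The end of treatment/follow up column will be utilized for subjects that come off protocol therapy", because of toxicity or progression. It continues: "If this occurs, subjects should have an end of treatment visit 30 days", with a window of ±7 days, after protocol therapy is discontinued. Footnote 14 of the Section 7 calendar gives the same timing. The tests listed for the visit include CTCs, serum bone turnover markers, and banked serum and plasma. Section 9.2 stains gamma-H2AX on the CTC slides, so it shares the CTC draw.

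**What may happen before the draw.** For radiologic progression or symptomatic deterioration, Section 7.10 says: "Such subjects can go on to other treatment outside the study as clinically indicated including continuation or initiation of radium-223 dichloride therapy". For PSA-defined castration resistance it says: "If no response to bicalutamide discontinuation, such subjects may receive other treatment outside the study as clinically indicated", again naming radium-223. For ADT toxicity it says: "Such subjects may receive other treatment outside the study as clinically indicated including continuation or initiation of radium-223 dichloride therapy". None of these permissions gives an interval or mentions the EOT draw. The bar on chemotherapy in Section 5.8 covers the treatment period only: "Cytotoxic chemotherapy is not allowed during protocol specified therapy".

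**How the samples are to be used.** Section 9.1 reports that "Radium-223 dichloride demonstrated similar declines in bone turnover markers in CRPC" and hypothesizes that "lower marker levels at end of treatment visit will be associated with improved survival". Section 9.2 uses gamma-H2AX to look for radiation-induced DNA damage in CTCs. Section 12.7 tests changes in bone markers between arms at each later time point.

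**The concern.** An EOT sample should describe the man's state at the end of ADT, with or without radium. With the draw 23 to 37 days after therapy stops, and the next treatment free to begin in that gap, it may instead describe the early effect of that treatment. The men sent to the EOT visit are those stopping for toxicity or progression, and progressing men are the ones most likely to need something else.

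Two analyses are exposed. In the EOT bone-marker comparison, a control man may already have had radium, and an Arm B man may have carried on with it off study. In the EOT–survival association, the next treatment can act on both sides: Section 9.1 says radium lowers bone markers, and Section 1.3 reports longer survival with radium in castration-resistant disease (hazard ratio for death 0.695). A low EOT marker level could then go with longer survival because of the next treatment, not the protocol treatment. For CTCs and gamma-H2AX, EOT is the only draw after Cycle 4 Day 1, so a sample affected in this way has no later replacement.

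**Working it through.** The plan gives no figure on this point to reproduce. The check is of timing and permissions.

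**Step 1: is the order of draw and treatment fixed anywhere?**

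| Place | Draw ordered relative to treatment? |
|---|---|
| Footnotes 10 and 11; Sections 7.2 and 7.3 (baseline and induction research bloods) | Baseline samples and the Day 1 bone-marker samples are specified before dosing |
| Footnotes 10, 11 and 14; Section 7.10 (EOT) | No ordering relative to the next treatment |
| Sections 9.1, 9.2 and 9.3 (EOT) | No ordering relative to the next treatment |
| Section 12.7 | No rule for samples taken after new treatment starts |

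The protocol controls the order at baseline and leaves it open at EOT.

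**Step 2: can a control man be treated with radium before his EOT draw?** The window is 30 − 7 = day 23 to 30 + 7 = day 37 after discontinuation. Suppose off-study radium starts on day s and is repeated every 28 days. The 28-day interval in Section 5.4 is borrowed for illustration only, and s is assumed. For a draw on day v:

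- doses received = floor((v − s)/28) + 1
- share of the first dose physically decayed = 1 − 0.5^((v − s)/11.4), with the 11.4-day half-life from Section 10.1

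| Start s | Draw on day 23 | Draw on day 30 | Draw on day 37 |
|---|---|---|---|
| 0 | 1 dose, 75% | 2 doses, 84% | 2 doses, 90% |
| 7 | 1 dose, 62% | 1 dose, 75% | 2 doses, 84% |
| 14 | 1 dose, 42% | 1 dose, 62% | 1 dose, 75% |

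The dose counts are the same at the 25-day minimum spacing. A control man could have had one or two doses before the sample is drawn.

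**Step 3: can the effect on the arm contrast be sized?** That would need the radium signal in Arm B at EOT. Radium is scheduled for Cycles 2 to 7, so the last planned dose is 6 × 28 = 168 days after Cycle 1 Day 1. Take progression times equal to the planning medians in Section 12.1, with 30.4 days per month:

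- 12 months: 365 − 168 = 197 days after the last dose, and 197/11.4 = 17 half-lives
- 19 months: 578 − 168 = 410 days after the last dose, and 410/11.4 = 36 half-lives

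The EOT visit comes about 30 days later still. A man in Arm B who stops at such times may show little or no radiation signal at EOT, whereas one who stops during radium treatment may show a good deal. The documents give neither the mix of such men nor the share in either arm who start new treatment before the draw. No size or direction follows.

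**The case against.** **No figure for the loss is supported.** A reader might infer that off-study radium in a share f of control men shrinks the arm contrast to 1 − f of its size and inflates the required sample by 1/(1 − f)². That assumes radium has the same effect in these controls as in Arm B at EOT, and that Arm B is untouched. Step 3 shows the first need not hold. Section 7.10 also allows radium to continue in Arm B, so the second need not hold either. A recently dosed control could even show more radiation signal than an Arm B man long past his last dose. This objection stands in full.

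**No planned gamma-H2AX comparison is spoiled.** Section 2.3 only asks to assess CTC numbers and gamma-H2AX, and Section 12.7 specifies no arm test for either. This stands; for these markers the consequence is difficulty of interpretation. On-treatment effects are also sampled earlier: CTCs at Cycle 4 Day 1, bone markers through Cycle 7.

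**Immediate switching is not stated.** A reader might infer that the protocol invites the next treatment at once. It sets no interval, which is different. For PSA-defined resistance, bicalutamide withdrawal may be tried first. That step does not count as going off treatment, however, so the gap before the EOT visit remains. Section 1.3 notes that radium was approved for symptomatic castration-resistant disease, which may limit how many controls start it early.

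**Other documents or data may cover it.** Collection details are deferred to a laboratory manual that is not supplied, but the manual cannot be assumed to override the protocol's stated 30-day timing. Concomitant medication is marked in the EOT column, and footnote 6 covers all medications, so start dates may be partly available. Footnote 13 asks for initiation of new anticancer therapy in Cycles 14 to 17; footnote 14 asks for medication data only where record review provides them.

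**The analyses are exploratory.** Section 9.1 says so, and bone-marker assays await funding. This limits the weight of the point without answering it.

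**Conclusion.** The point holds as a weakness in sample timing. Followed as written, the schedule can produce EOT research samples taken after one or more doses of a non-protocol treatment, in either arm. This confounds the EOT bone-marker comparison and the EOT–survival association, and clouds the EOT CTC and gamma-H2AX values. It is more than missing detail, because the 30-day timing itself opens the gap.

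Size and direction are unknown. They depend on how many men start new treatment within 23 to 37 days, which treatment it is, and how long before EOT the Arm B men had their last radium dose; the documents give none of these. The dose counts above rest on assumed start days and a borrowed interval, and show only that exposure is possible. The documents do not support a stated percentage loss, or a claim that the arms must be pulled together.

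The primary rPFS test does not use these samples and is unaffected. Because the affected analyses are exploratory and the change is cheap, this is a point to consider.

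**What to change.** In footnotes 10, 11 and 14 and in Section 7.10, require the EOT research bloods (CTC/gamma-H2AX, bone turnover markers, banked serum and plasma) to be drawn at or after discontinuation of protocol therapy but before the first dose of any non-protocol anticancer treatment. State that this treatment is not to be delayed for the draw. Keep the 30-day visit for adverse events, and align the laboratory manual.

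Record the start date of the first non-protocol anticancer treatment for every man with an EOT visit. Flag any sample drawn after that date. In Section 12.7, report the EOT bone-marker comparison and the EOT–survival analysis with and without flagged samples. Do not simply drop them: starting new treatment is a post-randomization event, and faster progressors may start soonest, so exclusion alone could bias the survival association.

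The cost is wording, one date field and a sensitivity analysis, with the same tubes. Kits must be on site when therapy stops, and the interval from last protocol dose to draw will vary between men, so it should be recorded.

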**8. CRITERIA FOR DISEASE EVALUATION AND ENDPOINT DEFINITIONS**  
RECIST 1.1 criteria will apply to only soft tissue lesions. PCWG2 criteria will apply to bone lesions and PSA values.

### **8.1 Measurability of lesions**

#### **8.1.1 Measurable disease**

All measurable lesions up to a maximum of 2 lesions per organ and up to 5 lesions in total, representative of all involved organs, should be identified as *target* lesions at baseline. Measurements must be provided for target measurable lesions, while presence or absence must be noted for non-target measurable and non-measurable disease.

1. Lesions that can be accurately measured in at least one dimension (longest diameter to be recorded) as  $\geq 2.0$  cm by chest x-ray, by  $\geq 1.0$  cm with CT or MRI scans, or  $\geq 1.0$  cm with calipers by clinical exam. All tumor measurements must be recorded in decimal fractions of centimeters (or millimeters).

The defined measurability of lesions on CT scan is based on the assumption that CT slice thickness is 0.5 cm or less. If CT scans have slice thickness greater than 0.5 cm, the minimum size for a measurable lesion should be twice the slice thickness.

2. Malignant lymph nodes are to be considered pathologically enlarged and measurable if they measure  $\geq 1.5$  cm in **SHORT AXIS** (greatest diameter perpendicular to the long axis of the lymph node) when assessed by scan (CT scan slice recommended being no greater than 0.5 cm).

#### **8.1.2 Non-measurable disease**

All other lesions (or sites of disease), including small lesions (longest diameter < 1.0 cm or pathologic lymph nodes with  $\geq 1.0$  cm to <1.5 cm short axis), are considered non-measurable disease. Bone lesions, leptomeningeal disease, ascites, pleural/pericardial effusions, lymphangitis cutis/pulmonitis, inflammatory breast disease, and abdominal masses (not followed by CT or MRI), are considered non-measurable, as are previously radiated lesions that have not progressed.

### 8.1.3 Notes on measurability

1. For CT and MRIs, the same type of scanner should be used and the image acquisition protocol should be followed as closely as possible to prior scans. Body scans should be performed with breath-hold scanning techniques, if possible.

PET-CT: At present, the low dose or attenuation correction CT portion of a PET-CT is not always of optimal diagnostic CT quality for use with RECIST measurements. However, if the site can document that the CT performed as part of a PET-CT is of identical diagnostic quality to a diagnostic CT, then the CT portion of the PET-CT can be used for RECIST measurements and can be used interchangeably with conventional CT.

2. Ultrasound: Ultrasound is not useful in assessment of lesion size and should not be used as a method of measurement.
3. Cystic lesions that meet the criteria for radiographically defined simple cysts should not be considered as malignant lesions (neither measurable nor non-measurable) since they are, by definition simple cysts.
4. If a target lesion becomes very small, some radiologists indicate that it is too small to measure. If the lesion is actually still present, a default measurement of 0.5 cm should be applied. If the radiologist believes the lesion has gone, a default measurement of 0.0 cm should be recorded.

## 8.2 Progression Criteria

**8.2.1 PSA progression** is defined by two consecutive increases in PSA over the nadir PSA, at least two weeks apart AND an absolute increase of at least 2 ng/mL from the nadir PSA (or from baseline PSA if there was no drop in PSA after starting treatment).

**8.2.2 Radiographic Skeletal progression on bone scan** is defined as 2 or more new lesions on radionuclide bone scans (PCWG2 criteria). Should two or more new bone lesions be evident at the first imaging assessment (at end of protocol specified therapy), two or more additional new lesions must be evident on a confirmatory assessment at least 6 weeks later.

A bone scan may be ordered at the discretion of the treating physician within the first 7 months of protocol treatment for symptoms e.g. bone pain. If new bone lesions appear in the absence of a rising PSA within the first 7 months of protocol treatment, the site investigator at the institution must consult the sponsor-investigator (via the HCRN Project Manager) to discuss the possibility of tumor flare.

For bone disease documented on bone scan only, increased uptake does not constitute unequivocal progression. However, increase in the soft tissue component of a lesion as measured by CT or MRI would constitute progression.

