The trial was stopped in early 2011 when a planned interim analysis by an independent data safety and monitoring committee from the trial detected that men randomized to radium-223 had statistically significantly better overall survival than men assigned to receive the placebo. Median overall survival was 14.9 months for the men assigned to receive radium-223 and 11.3 months for those assigned to the placebo (HR for death 0.695, 95% CI 0.552-0.875, p=0.002). An overall survival benefit with radium-223 was seen in all subgroups of men analyzed—for example, men benefited whatever the extent of their disease.

In the ALSYMPCA study, increase in PSA level was defined as a relative increase of  $\geq 25\%$  from the baseline level and an absolute increase of  $\geq 2$  ng per milliliter at  $\geq 12$  weeks, in patients with no decrease in the PSA level from baseline, or a relative increase of  $\geq 25\%$  and an absolute increase of  $\geq 2$  ng per milliliter above the nadir, confirmed  $\geq 3$  weeks later, in patients with an initial decrease from baseline. Radium-223 significantly prolonged the time to an increase in PSA level thus defined (HR 0.64; 95% CI, 0.54 to 0.77; P<0.001). A 30% or greater reduction in PSA blood levels at week 12 was achieved in 16% of patients in the radium-223 group and in 6% of patients in the placebo group (P<0.001).

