### **8.6 Time to Castration Resistance**

Castration resistant prostate cancer is defined as either PSA progression or radiographic progression. Time to Castration resistance will be counted from start of ADT (first LHRH agonist/antagonist/surgical castration) to development of castration resistance by either criterion:

- **PSA progression** per 10.2.1. Castration resistance will be determined to have occurred at the time of the first PSA increase.

- **Radiographic progression** Castration resistance will be determined to have occurred at the time of the first imaging assessment showing progression not the confirmatory scan (for bone lesions).

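### PSA progression needs no relative rise, so above a nadir of 8 ng/mL a high but stable PSA can count as PSA progression and castration resistance

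*Combined protocol and SAP*

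**What the plan says.** Section 8.2.1 sets the PSA event as "two consecutive increases in PSA over the nadir PSA, at least two weeks apart AND an absolute increase of at least 2 ng/mL" from nadir, "or from baseline PSA if there was no drop in PSA after starting treatment". It gives no percentage.

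Three other sections depend on this rule or repeat it:

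- **8.4** counts PSA progression as an event for PSA progression-free survival (PSA-PFS).
- **8.6** states: "Castration resistant prostate cancer is defined as either PSA progression or radiographic progression". On dating it says: "Castration resistance will be determined to have occurred at the time of the first PSA increase". It sets no testosterone condition. It cites a section 10.2.1 for PSA progression, but the definition stands in 8.2.1.
- **7.10** uses the same rule to end protocol therapy: "Castration resistant prostate cancer is defined as two consecutive increases in PSA over the nadir PSA, at least two weeks apart", again with the 2 ng/mL rise. Here it applies "If there is development of castration-resistant prostate cancer by PSA criteria in conjunction with castration range serum testosterone level".

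Two further places bear on the threshold. The opening of Section 8 says "PCWG2 criteria will apply to bone lesions and PSA values", without reproducing the PCWG2 PSA rule. Section 1.3 reports that in the cited phase 3 radium trial "increase in PSA level was defined as a relative increase of" at least 25%, together with an absolute rise of at least 2 ng/mL and that trial's own timing conditions.

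**The concern.** A fixed 2 ng/mL step is a demanding threshold when the nadir is low and a trivial one when it is high. Followed exactly, 8.2.1 turns a nadir of 100 followed by 101 and 102 into PSA progression, and 8.6 turns it into castration resistance dated to the value of 101.

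The protocol's other progression rules based on a measured quantity do scale with its level. Soft-tissue progression needs 20% as well as 0.5 cm (8.2.3). Alkaline phosphatase progression needs 25% as well as a value above the upper limit of normal (8.11). Only the PSA rule has no relative part.

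Sections 12.6 and 12.7 keep PSA out of the primary analysis, but PSA-PFS and time to castration resistance are both tested between arms and reported by Kaplan-Meier methods. Events produced by variation rather than disease lower the 2-year PSA-PFS proportion, shorten the time to castration resistance and, where they arise regardless of treatment, blur the comparison. They fall on subjects with a poor PSA response. Because 7.10 repeats the rule, such an event can also end protocol therapy and open other treatment, including radium-223 for control subjects.

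**Working it through.** No stated sample size, power or event count depends on this definition, so there is no plan figure to reproduce.

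**Step 1: the threshold as a percentage.** Relative threshold = 100 × 2 / nadir.

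| Nadir (ng/mL) | 2 | 4 | 8 | 10 | 20 | 50 | 100 |
|---|---|---|---|---|---|---|---|
| 2 ng/mL as % of nadir | 100 | 50 | 25 | 20 | 10 | 4 | 2 |

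A 25% requirement therefore adds nothing at a nadir of 8 or less, and becomes the binding condition above 8. This step needs no assumption.

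**Step 2: false events when PSA is truly flat.** Inputs:

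- From the documents: the 8.2.1 rule, and PSA on Day 1 of each cycle through Cycle 12 (5.6). Nine monthly values correspond roughly to Cycles 4 to 12.
- Assumed: the within-subject coefficient of variation (CV), which the documents do not give; 3%, 5% and 10% are shown.

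Model: value = L × exp(Z), with Z normal, variance s² = ln(1 + CV²) and mean −s²/2, independent between visits. The nadir N is the lowest value up to two visits before the current one. There were 40,000 series per setting; repeat runs differ by up to about 1 percentage point.

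The text leaves the meaning of consecutive increases open, so two readings bracket it:

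- *Lenient:* two consecutive values above N, the second at least 2 ng/mL above N.
- *Strict:* two successive rises starting from the nadir visit itself, the second at least 2 ng/mL above N.

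Chance of a false event as written (strict–lenient):

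| Flat PSA | CV 3% | CV 5% | CV 10% |
|---|---|---|---|
| 20 | 5–15% | 27–65% | 49–93% |
| 50 | 43–87% | 53–95% | 57–98% |
| 100 | 54–97% | 57–98% | 57–99% |

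At a flat PSA of 4 the chance is under 1% at every CV shown.

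**Step 3: adding a 25% rise.** The result depends on which values must meet it.

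- *Only the second value held to 25%* (PSA 50, strict–lenient): about 0.5–2% at CV 5%, but 21–55% at CV 10%.
- *Both values held to 25% and 2 ng/mL:* about 0.1% at CV 5%. At CV 10% it is about 21%, or about 13% if the second value must also exceed the first.

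Over 14 values instead of nine, the rule with both values held to the thresholds gives about 0.3% at CV 5% and 40% at CV 10%. It is a large improvement but not immunity if variation is high.

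**Step 4: who is exposed.** Section 1.1 cites a trial in which 74% reached PSA below 4 on combined androgen deprivation, leaving 100 − 74 = 26% who did not. That is a loose upper guide from another trial. The share with a nadir above 8 would be smaller and is not stated.

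**The case against.** The probabilities rest on an assumed CV, a hypothetical PSA that stays flat for nine visits, and a phrase with several readings. They range from 5% to 99%, the exposed share is unknown, and no effect on either arm's PSA-PFS or time to castration resistance has been computed. All of that stands. It limits the claim to what can happen; it does not make the rule adequate, because at PSA 50 even the strict reading with 3% variation flags 43% of stable subjects.

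The 25% rule in Section 1.3 is background about a castration-resistant population, and nothing binds this trial to it. That also stands; the rule serves only as a threshold that the protocol itself describes. The castrate-testosterone condition in 7.10 is a safeguard, but it does not filter PSA variation.

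A reader might go further in three ways, none of which the documents support:

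- *That 8.2.1 departs from PCWG2.* The PCWG2 PSA rule is not reproduced, so this cannot be checked here.
- *That a false PSA event stops scheduled assessments.* Section 12.6 asks for every effort to continue tumor assessments on schedule when treatment stops for reasons other than death or investigator-assessed progression. Section 7.10 keeps these subjects in follow-up for 2 years from randomization.
- *That the primary endpoint is directly affected.* The rPFS definition and its 140 events do not use PSA. Earlier discontinuation could influence later treatment, but that route is indirect and unquantified.

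**Conclusion.** The point holds. Sections 8.2.1, 7.10 and 8.6 contain no relative rise, and above a nadir of 8 ng/mL the fixed step falls below 25%, reaching 2% at a nadir of 100. A subject with a high, stable PSA can therefore be counted as PSA-progressed and castration-resistant. At an assumed 5% CV the chance over nine monthly values is at least about one in four at PSA 20 and about one in two at PSA 50, on the reading most favorable to the plan.

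The missing percentage is certain from the text. The size of the effect depends on the assumed CV, the flat-PSA model and the reading of consecutive increases. The direct effect is confined to PSA-PFS and time to castration resistance, in an unstated minority of subjects if the figure cited in Section 1.1 is a guide. It is worth correcting and does not threaten the primary analysis.

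**What to change.** For the endpoint definitions only, amend 8.2.1:

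- Keep two consecutive values at least two weeks apart, and require each to be at least 25% and at least 2 ng/mL above nadir (or above baseline if PSA never declined).
- State that this is what consecutive increases means.
- Report PSA-PFS and time to castration resistance under the current definition as a sensitivity analysis.

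This takes the relative-plus-absolute threshold that Section 1.3 describes, without that trial's timing conditions.

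Separately, the sponsor should reconcile 7.10, 8.2.1 and 8.6. Section 7.10 repeats the current rule and adds a castrate-testosterone condition that 8.6 lacks. This review takes no position on the discontinuation rule.

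The text change is short, but it has costs. True progressors with a nadir above 8 will have later event dates. Holding both values to 2 ng/mL can also delay an event at a lower nadir when the first rise is small. Some PSA values may be missing: a subject who leaves therapy under 7.10 before meeting the amended endpoint has follow-up PSA only where medical records provide it. The sensitivity analysis shows how far the results depend on the change.
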